#### **Study Design:**

This study will be conducted as a multicenter, randomized, double-blind, placebo-controlled Phase 2b trial to assess the efficacy, safety, tolerability, and PK of liafensine in DGM4-stratified TRD patients. The study includes an up to 21-day screening period.

Approximately 180 patients with TRD who meet all eligibility criteria will be randomized in a 1:1:1 ratio to receive either liafensine 1 mg QD, liafensine 2 mg QD, or placebo QD for 6 weeks. Approximately 150 randomized patients carrying genotype GG at DGM4 (DGM4-positive) and approximately 30 randomized patients carrying genotype AA or AG at DGM4 (DGM4-negative) will be enrolled in this study. DGM4 status (positive vs negative) of randomized patients will be blinded to the sites, the patients, and sponsor. An Interactive Response Technology (IRT) system will be used for blinding DGM4 status, and to achieve the planned randomization ratio of DGM4-positive:DGM4-negative patients by randomly excluding most screened DGM4-negative patients (~80%). Randomization will be stratified by DGM4 status (positive vs negative) and region (North America vs Other). Patients who complete the study or discontinue after randomization will have two post-study follow-up visits (14 days after the last administered dose of study drug, and 28 days after the last administered dose of study drug); the 2nd follow-up visit will be conducted via phone call. Every effort will be made to ensure that the protocol-required tests and procedures are completed.

During the study, safety will be assessed on the basis of spontaneously reported AEs; the DESS; physical, neurological, and psychiatric examinations (including the C-SSRS); vital signs including supine and standing blood pressure and heart rate; weight; 12-lead ECGs; clinical laboratory test results; serum and urine pregnancy tests (females of childbearing potential only); and concomitant medication assessments. In addition to blood samples collected for PK, additional blood samples may be collected for determination of plasma concentrations of liafensine and its primary metabolite in association with the evaluation of safety signals.

The overall study design is shown in Figure 1. The schedule of study assessments is presented in Table 1 with the clinical laboratory tests shown in Table 3.

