In the Phase 2b studies conducted by Bristol-Myers Squibb (BMS), there were no significant differences noted between the treatment groups in the decrease (improvement) of the mean Montgomery-Åsberg Depression Rating Scale (MADRS) total score. In an effort to identify a potential pharmacogenomic biomarker of response to liafensine, Denovo Biopharma LLC (Denovo) has conducted a genome-wide scan with human whole genome single nucleotide polymorphism (SNP) arrays using germline deoxyribonucleic acid (DNA) extracted from blood samples of patients in BMS Studies CN162006 and CN162007. From this genome-wide screening, SNP rs12217173 was identified as strongly associated with treatment response to liafensine (p =  $6.6 \times 10^{-8}$ ). Patients with a GG genotype at rs12217173 showed significantly better response to liafensine compared to patients with an AA or AG genotype, or patients in the control arm (duloxetine or escitalopram). These findings were replicated using a separate validation sample set. Liafensine treatment effects in patients with the GG genotype were comparable for the 0.5 to 2 mg QD flexible doses in the CN162006 study and for the 1 mg QD and 2 mg QD doses in the CN162007 study. These combined data showed that patients with the GG genotype had a 4.7-point difference in MADRS total score decrease from baseline in the liafensine arm vs the control arm (p = 0.025), while patients with the AA or AG genotype at rs12217173 did not show an improved treatment effect in the liafensine arm vs the control arm

 BMS-820836-03 was selected for the dosage form development and is also referred to as BMS-820836.

(MADRS 0.3-point difference, p = 0.74). Moreover, patients carrying different genotypes at rs12217173 did not exhibit different treatment responses to duloxetine or escitalopram. Thus, SNP rs12217173 appears to be a pharmacogenomic biomarker specific for liafensine; Denovo has termed rs12217173 as "DGM4" (Denovo Genomic Marker 4) and the GG genotype of DGM4 is defined as DGM4 positive, whereas the AA or AG genotype of DGM4 is defined as DGM4 negative.

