#### 3. INVESTIGATIONAL PLAN

# 3.1. Overall Study Design

This study will be conducted as a multicenter, randomized, double-blind, placebo-controlled Phase 2b trial to assess the efficacy, safety, tolerability, and PK of liafensine. The study includes an up to 21-day screening period (the screening period may exceed 21 days if a prolonged washout is required).

[figure not shown]
Approximately 180 patients with TRD who meet all eligibility criteria will be randomized in a 1:1:1 ratio to receive either liafensine 1 mg QD, liafensine 2 mg QD, or placebo QD for 6 weeks. Approximately 150 randomized patients will be genotype GG for DGM4 (DGM4-positive) and approximately 30 randomized patients will be genotype AA or AG for DGM4 (DGM4-negative). DGM4 status (positive vs negative) of randomized patients will be blinded to the sites, patients, and sponsor. An Interactive Response Technology (IRT) system will be used for blinding to DGM4 status, and to achieve the correct randomization ratio of DGM4-positive:DGM4-negative patients by randomly excluding most screened DGM4-negative patients (~80%). Randomization will be stratified by DGM4 status (positive vs negative) and region (North America vs Other). Patients who complete the study or discontinue after randomization will have 2 post-study follow-up visits (14 days after the last administered dose of study drug, and 28 days after the last administered dose of study drug, phone call.

During the study, safety will be assessed on the basis of spontaneously reported AEs; the Discontinuation-Emergent Signs and Symptoms scale (DESS); physical, neurological, and psychiatric examinations (including the Columbia-Suicide Severity Rating Scale [C-SSRS]); vital signs including orthostatic changes in blood pressure and heart rate; weight; 12-lead electrocardiograms (ECGs); clinical laboratory test results; serum and urine pregnancy tests (females of childbearing potential only); and concomitant medication assessments. In addition to blood samples collected for PK, additional blood samples may be collected for determination of plasma concentrations of liafensine and its primary metabolite in association with the evaluation of safety signals.

The overall study design is shown in Figure 1. The schedule of study assessments is presented in Table 1 with the clinical laboratory tests shown in Table 3.

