# 3.4. Sample Size Justification

Eligible patients will be randomized 1:1:1 to receive liafensine 1 mg QD, liafensine 2 mg QD, or placebo QD. The primary analysis is to assess treatment difference in MADRS total score change from baseline (Visit 3, Day -1) to Visit 7 (Day 42), between the combined liafensine 1 mg QD and 2 mg QD doses vs placebo, in DGM4-positive patients. A sample size of 47 randomized DGM4-positive patients per arm is sufficient to detect a 4.5-unit difference between the combined liafensine 1 mg QD and 2 mg QD treatment groups and the placebo treatment group in the change in MADRS total score with 80% power at the 2-sided 0.05 alpha level, assuming a standard deviation of 9 units.

To compensate for potential loss of power due to randomized patients who do not take at least one dose of study drug or who do not have a post-randomization efficacy evaluation (~5%), a total of approximately 150 DGM4-positive patients (50 DGM4-positive patients per arm) will be randomized.

To examine trend in the total patient population and in the subgroup of DGM4-negative patients in order to evaluate DGM4 as a potential biomarker for predicting response to liafensine, approximately 20% additional DGM4-negative patients (10 per arm, total approximately 30) will also be randomized. The sample size of 30 randomized patients in the DGM4-negative group is not estimated based on formal statistics in terms of power and alpha level.

Sample size re-estimation may be conducted if the percentage of missing data at Day 42 visit is higher than expected and/or if the observed variance is higher than the one assumed in the sample size estimation.

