## 4.1. Subject Inclusion Criteria

Patients must meet all the following inclusion criteria to be eligible for enrollment into the study:

- 1. Provide signed informed consent which includes pharmacogenomic (PGx) testing.
- 2. Have a diagnosis of MDD without psychotic features, according to the *Diagnostic and Statistical Manual of Mental Disorders*, 5th Edition (DSM-5) criteria, based on clinical assessment and confirmed by the Mini International Neuropsychiatric Interview (MINI).
- 3. TRD documented in the Massachusetts General Hospital (MGH) Antidepressant Treatment Response Questionnaire (ATRQ) (5-year version). That is:
  - a. clinically meaningful inadequate response (estimated < 50% improvement per investigator/patient consensus and documented by the investigator) with:
    - 1) at least 2 treatment courses with antidepressant regimens;
    - 2) used at least 2 different pharmacologic treatment classes (eg, SSRI, SNRI, TCA, MAOI, atypical); or if only one class treatment is used, at least one combination treatment course;
    - 3) the doses have been given at accepted therapeutic doses for an adequate duration (at least 6 weeks), per product label;
    - 4) One of these inadequate response must occur within the current episode.

**Note**: non-pharmacological treatment (eg, cognitive behavioral therapy, electroconvulsive therapy, repetitive transcranial magnetic stimulation, vagus nerve stimulation, acupuncture) are not counted as treatment regimen.

- 4. To be eligible, patients must have DGM4 genotype results obtained from the designated Clinical Laboratory Improvement Amendments (CLIA) lab, and all eligible DGM4-positive patients and about 20% DGM4-negative patients will be randomly included by an IRT system in order to achieve the appropriate randomization ratio of DGM4-positive vs negative patients.
- 5. Pregnancy conception limitations

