## 7.1.2. Study Treatment Evaluations and Procedures

#### 7.1.2.1. Screening 1/Screening 2 Procedures (Visit 1 and Visit 2)

Unless otherwise noted below, all screening procedures, aside from DGM4 genotyping (performed prior to Day -21), must be performed within 21 days prior to randomization.

Screening 1 and Screening 2 procedures will be conducted over two visits as detailed in Table 1.

Screening 2 will only be performed after the initial eligibility including PGx (DGM4 status) is confirmed.

Laboratory testing and the assessment of vital signs can be repeated for up to 3 occurrences after Visit 2 to see if values return to normal range, but any abnormality must be resolved by the Baseline Visit.

All procedures as presented in Table 1 must be completed, including:

## Visit 1

- Brief informed consents
- Inclusion/exclusion criteria preliminary determination (not include MINI and ATRQ)
- A complete medical history

- Demographics
- Preliminary diagnosis checklist
- Biomarker: blood draw for DGM4 status
- Pregnancy test
- An assessment of adverse events

#### Visit 2

- Full informed consent
- Inclusion/exclusion criteria determination (continued)
- Psychiatric evaluations (MINI and ATRQ)
- Blood draw for clinical laboratory evaluations
- Complete physical and neurological examinations
- PRDF Checklist
- CGI-S
- MADRS
- HAMD-17
- C-SSRS, baseline/screening version
- Vital signs including supine (after at least 5 min rest) and standing (after 1 min and 3 min standing), blood pressure and heart rate
- Body weight and height
- Single 12-lead ECG will be performed
- Urinalysis (on-site unless macro-findings are observed and central lab assessment is required)
- Urine drug screen (on-site)
- Prior medications
- Assessment of adverse events

Note: Rater 1 is to assess HAMD-17 and MADRS; rater 2 is to assess CGI-S after reviewing PRDF Checklist; the rest of scales maybe collected by either rater.

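### Does excluding about 80% of screened DGM4-negative patients fail to deliver the planned 150:30 mix?

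*Protocol*

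**What the plan says.** Protocol 3.1 sets about 180 randomized patients, about 150 of them DGM4-positive (GG) and about 30 DGM4-negative (AA or AG). The IRT is "to achieve the correct randomization ratio of DGM4-positive:DGM4-negative patients by randomly excluding most screened DGM4-negative patients (~80" percent). The synopsis has the same figure ("randomly excluding most screened DGM4-negative patients (~80" percent), and Protocol 5.5 and SAP 2.1 repeat it. Inclusion criterion 4 in Protocol 4.1 puts it the other way round: "all eligible DGM4-positive patients and about 20% DGM4-negative patients will be randomly included by an IRT system".

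A second 20% appears in Protocol 3.4, where "approximately 20% additional DGM4-negative patients (10 per arm, total approximately 30) will also be randomized". That is 30 relative to 150. The same section says that the 30 does not rest on a power calculation.

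On timing, Protocol 7.1.2.1 says that "Screening 2 will only be performed after the initial eligibility including PGx (DGM4 status) is confirmed". Protocol 5.5 has an independent unblinded team tell the sponsor how many DGM4-positive patients have been enrolled. Neither document gives the proportion of patients expected to be GG.

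**The concern.** The fraction of negatives to discard depends on how common GG is among the patients genotyped. That input is absent, so the 80% cannot be derived from the documents. The keep rate of 20% (of screened negatives) and the add-on of 20% (30 relative to 150) are different quantities that agree only when the two genotype groups are equally common, which invites the suspicion that one was taken for the other.

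The earlier-study results strengthen the suspicion. Protocol 1.2.1 reports that "patients with the GG genotype had a 4.7-point difference in MADRS total score decrease from baseline in the liafensine arm vs the control arm", with p = 0.025, and for AA or AG patients "MADRS 0.3-point difference, p = 0.74". The smaller difference comes with a much smaller implied standard error, which suggests that GG patients were a minority.

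If 80% were applied literally in a population with few GG patients, the negatives randomized would exceed 30, perhaps several-fold, and the total would exceed 180. The positive-versus-negative comparison and the summaries pooling both groups would then rest on a different mix from the one planned.

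**Working it through.** **The mix identity.** Let g be the GG share among genotyped patients and k the share of negatives kept. All positives are kept, and both groups are assumed to pass Visit 2 equally often. Then positives : negatives = g : k(1 − g). Setting this to 150:30 = 5 gives g = k/(k + 0.2).

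- k = 0.15 (85% excluded): g = 0.15/0.35 = 43%
- k = 0.20 (80% excluded): g = 0.20/0.40 = 50%
- k = 0.25 (75% excluded): g = 0.25/0.45 = 56%

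The plan's 80% cannot be reproduced forwards, because g is not given. The neighbouring figures do reproduce: 47/0.95 = 49.5, so 50 per arm and 150 in all; 30/150 = 20%.

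**What Protocol 1.2.1 implies about g.** The comparison group there was "patients in the control arm (duloxetine or escitalopram"). Converting the two-sided p-values to z and dividing:

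- GG: z = 2.241, SE = 4.7/2.241 = 2.10
- AA or AG: z = 0.332, SE = 0.3/0.332 = 0.90
- variance ratio R = (2.097/0.904)² = 5.38, or 3.69 to 8.29 when all four reported figures vary within rounding

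With s the ratio of the GG SD to the AA/AG SD, and a the factor by which a less even arm split in GG inflates its variance, g = 1/(1 + R/(a·s²)).

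- s = 1, a = 1: g = 1/(1 + 5.38) = 16% (11% to 21% from rounding)
- s = 1.5, a = 1, R = 3.69: g = 1/(1 + 3.69/2.25) = 38%
- s = 1.5, a = 1.33, R = 3.69: 3.69/(1.33 × 2.25) = 1.23, so g = 1/2.23 = 45%

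The value a = 1.33 corresponds to 75% of GG patients and 50% of AA/AG patients being on liafensine: (0.5 × 0.5)/(0.75 × 0.25) = 1.33. The last line is an extreme corner, but it lies inside the 43% to 56% band. Central values are lower.

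**Consequences for the count of negatives.** Negatives per 150 positives = 150·k(1 − g)/g. Exclusion needed for 5:1 = 1 − 0.2g/(1 − g).

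| g | 80% excluded | 85% excluded | Exclusion needed |
|---|---|---|---|
| 16% (0.157) | 161 | 121 | 96% |
| 30% | 70 | 53 | 91% |
| 38% (0.379) | 49 | 37 | 88% |
| 45% (0.448) | 37 | 28 | 84% |
| 50% | 30 | 22.5 | 80% |

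Over the assumptions tried, literal use of 80% gives anything from a modest excess to a several-fold one. The documents do not settle which.

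**What the plan does with the percentage.** Every passage that gives the exclusion percentage gives the target mix as its purpose, and the percentage is marked as approximate. The counts of about 150, 30 and 180 stand on their own. The IRT holds genotype, since randomization is stratified by it. The sponsor receives the positive count and can subtract it from the total randomized, so a drift in negatives would be visible. SAP 5.1.1 already tabulates the number screened, screen failures attributed to DGM4 status and the number randomized. Positives are not excluded on DGM4 status, so that failure row counts the discarded negatives.

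**The case for a change.** The best case for a change runs as follows. Selection acts before Visit 2, so unequal pass rates are unlikely to rescue the ratio: at g = 16%, positives would have to pass (1 − 0.157)/0.157 = 5.4 times as often as negatives, and at 30%, 2.3 times. No cap or adjustment rule for negatives is written down. SAP 5.4 presents efficacy for both genotype groups combined as well as separately, and that mix would move from 83:17 (150:30) to about 48:52 (150:161). Extra negatives would be treated although the earlier data showed no advantage for that genotype. Stating the expected GG share would cost a sentence.

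Part of this stands. The share is missing, the identity is exact, the central indirect estimate is below 50%, and the two uses of 20% are easy to confuse on a quick reading. The rest does not carry a change. The overrun needs an approximate percentage to be followed past the stated 30 and 180. The IRT specification, where a cap would normally sit, is not among the documents, so its absence there cannot be inferred. Protocol 1.2.4 and 1.2.5 refer to an Investigator's Brochure for the earlier studies; it was not available and may give the genotype frequency. An extra disposition row for the retention fraction would largely repeat SAP 5.1.1. It would add only the retained negatives who later failed on other grounds.

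**Conclusion.** No change follows. The 80% fits 150:30 only at a GG share near 50%, assuming equal Visit 2 pass rates, and that share is undocumented. The evidence against 50% is a back-calculation giving 16% at its centre and up to about 45% when the favourable assumptions are combined. It also assumes that the patients screened resemble those in the earlier studies. A several-fold excess of negatives is possible but not established.

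The gap is one that those running the trial fill sensibly by steering the approximate fraction towards the stated counts. The primary analysis, confined to DGM4-positive patients, is the same at any number of negatives. Efficacy in DGM4-negative patients is exploratory, mainly descriptive and not powered, so a different count would alter its precision but not its validity. SAP version 2 precedes database lock and already mentions a death in the study, so enrolment may be over, in which case rewording the exclusion percentage would have no practical effect.

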# 3.2. Methodology

This is a randomized, double-blind, placebo-controlled Phase 2b trial to assess the efficacy, safety, tolerability, and PK of liafensine. The primary endpoint is change in MADRS total score from baseline (Visit 3, Day -1) to Visit 7 (Day 42) in DGM4-positive patients. The primary analysis will be conducted to assess the superiority of liafensine treatment (combined liafensine 1 mg QD and 2 mg QD doses) vs placebo in randomized patients who are DGM4-positive.

# 3.3. Study Duration and Follow-up

The duration of participation for individual patients will be up to 91 days or longer, including an up to 21-day screening period (screening period may exceed 21 days if a prolonged washout is required), a 6-week double-blind treatment period, and 2 post-study follow-up visits (at 14 days and 28 days after the last dose of study drug); the 2nd follow-up visit will be conducted via phone call (Figure 1).

# 3.4. Sample Size Justification

Eligible patients will be randomized 1:1:1 to receive liafensine 1 mg QD, liafensine 2 mg QD, or placebo QD. The primary analysis is to assess treatment difference in MADRS total score change from baseline (Visit 3, Day -1) to Visit 7 (Day 42), between the combined liafensine 1 mg QD and 2 mg QD doses vs placebo, in DGM4-positive patients. A sample size of 47 randomized DGM4-positive patients per arm is sufficient to detect a 4.5-unit difference between the combined liafensine 1 mg QD and 2 mg QD treatment groups and the placebo treatment group in the change in MADRS total score with 80% power at the 2-sided 0.05 alpha level, assuming a standard deviation of 9 units.

To compensate for potential loss of power due to randomized patients who do not take at least one dose of study drug or who do not have a post-randomization efficacy evaluation (~5%), a total of approximately 150 DGM4-positive patients (50 DGM4-positive patients per arm) will be randomized.

To examine trend in the total patient population and in the subgroup of DGM4-negative patients in order to evaluate DGM4 as a potential biomarker for predicting response to liafensine, approximately 20% additional DGM4-negative patients (10 per arm, total approximately 30) will also be randomized. The sample size of 30 randomized patients in the DGM4-negative group is not estimated based on formal statistics in terms of power and alpha level.

Sample size re-estimation may be conducted if the percentage of missing data at Day 42 visit is higher than expected and/or if the observed variance is higher than the one assumed in the sample size estimation.

## 3.5. Number of Subjects

Approximately 180 patients will be enrolled in the study.

# 3.6. Treatment Assignment

Patients who meet all of the inclusion criteria and none of the exclusion criteria will be randomized through an IRT system in a 1:1:1 ratio to receive either liafensine 1 mg QD, liafensine 2 mg QD, or placebo QD for 6 weeks.

# 3.7. Criteria for Study Termination

The sponsor may decide to terminate the study at any time. Furthermore, the sponsor will consider recommendations provided by an external IDMC with regards to study continuation, modification, and/or termination (Section 7.6).

#### 4. SELECTION AND WITHDRAWAL OF PATIENTS

This study can fulfill its objectives only if appropriate patients are enrolled. The following eligibility criteria are designed to select patients for whom participation in the study is considered appropriate. All relevant medical and nonmedical conditions should be taken into consideration when deciding whether a patient is suitable for this protocol.

Patient eligibility should be reviewed and documented by an appropriate member of the investigator's study team before patients are included in the study.

## 4.1. Subject Inclusion Criteria

Patients must meet all the following inclusion criteria to be eligible for enrollment into the study:

- 1. Provide signed informed consent which includes pharmacogenomic (PGx) testing.
- 2. Have a diagnosis of MDD without psychotic features, according to the *Diagnostic and Statistical Manual of Mental Disorders*, 5th Edition (DSM-5) criteria, based on clinical assessment and confirmed by the Mini International Neuropsychiatric Interview (MINI).
- 3. TRD documented in the Massachusetts General Hospital (MGH) Antidepressant Treatment Response Questionnaire (ATRQ) (5-year version). That is:
  - a. clinically meaningful inadequate response (estimated < 50% improvement per investigator/patient consensus and documented by the investigator) with:
    - 1) at least 2 treatment courses with antidepressant regimens;
    - 2) used at least 2 different pharmacologic treatment classes (eg, SSRI, SNRI, TCA, MAOI, atypical); or if only one class treatment is used, at least one combination treatment course;
    - 3) the doses have been given at accepted therapeutic doses for an adequate duration (at least 6 weeks), per product label;
    - 4) One of these inadequate response must occur within the current episode.

**Note**: non-pharmacological treatment (eg, cognitive behavioral therapy, electroconvulsive therapy, repetitive transcranial magnetic stimulation, vagus nerve stimulation, acupuncture) are not counted as treatment regimen.

- 4. To be eligible, patients must have DGM4 genotype results obtained from the designated Clinical Laboratory Improvement Amendments (CLIA) lab, and all eligible DGM4-positive patients and about 20% DGM4-negative patients will be randomly included by an IRT system in order to achieve the appropriate randomization ratio of DGM4-positive vs negative patients.
- 5. Pregnancy conception limitations
  - Female patients must be postmenopausal or surgically sterile or, if of childbearing potential and the partner is not vasectomized (6 months minimum), must agree to use a medically acceptable form of contraception from the time of signing the informed consent form (ICF) through at least 60 days following the last administration of study drug. If only the barrier method is used, a double barrier must be employed. Postmenopausal women must have had ≥ 24 months of spontaneous amenorrhea. Surgically sterile women are defined as those who have had a hysterectomy, bilateral ovariectomy, or bilateral tubal ligation. All women of childbearing potential must have a negative pregnancy test result before administration of study drug.
  - Male patients must be biologically incapable of having children (eg, vasectomized) or must agree to use the above forms of birth control for themselves and their partner from the time of signing the ICF through at least 120 days following the last administration of study drug.

- 6. Be fluent in the local language.
- 7. Male or female aged 18 to 70, inclusive, at time of Visit 1.
- 8. Have a HAMD-17 total score  $\geq 21$  at screening and baseline.
- 9. Be willing to discontinue the use of antidepressant drugs (including over-the-counter medications to treat depression [eg, St John's Wort]) at least 5 half-lives (or at least 1 week for herbal or other over-the-counter medications for depression) prior to baseline (Day -1). For fluoxetine, a washout period of at least 3 weeks for ≤ 20 mg/day and at least 4 weeks for > 20 mg/day is required.

